4.11 OFF-STUDY CRITERIA

- Screen failure
- Patient begins another LMB trial which allows data collection
- Unwillingness to continue follow-up or provide follow-up data.

4.12 LOST TO FOLLOW-UP

A participant will be considered lost to follow-up if he or she fails to return for 3 consecutive scheduled visits and is unable to be contacted by the study site staff.

The following actions must be taken if a participant fails to return to the clinic for a required study visit:

- The site will attempt to contact the participant and reschedule the missed visit within 2 weeks and counsel the participant on the importance of maintaining the assigned visit schedule and ascertain if the participant wishes to and/or should continue in the study.
- Before a participant is deemed lost to follow-up, the investigator or designee will make every effort to regain contact with the participant (where possible, 3 telephone calls and, if necessary, a certified letter to the participant's last known mailing address or local equivalent methods). These contact attempts should be documented in the participant's medical record or study file.
- Should the participant continue to be unreachable, he or she will be considered to have withdrawn from the study with a primary reason of lost to follow-up.

5 HUMAN SUBJECTS PROTECTIONS

5.1 RATIONALE FOR SUBJECT SELECTION

Selection is based on gender, ethnic background or race.

Subjects from both genders and all racial/ethnic groups are eligible for this study if they meet the eligibility criteria. To date, there is no information that suggests that differences in drug metabolism or disease response would be expected in any one patient group. Efforts will be made to extend accrual to a representative population, but in this preliminary study, a balance must be struck between patient safety considerations and limitations on the number of patients exposed to a potentially toxic treatment on the one hand and the need to explore gender and ethnic aspects of clinical research on the other. If differences in the outcome which correlate with gender or ethnic identity are noted, accrual may be expanded or a follow-up study may be written to investigate these differences.

5.1.1 Justification for Exclusions

Patients with hepatitis C positivity are excluded from this trial because of the concern that LMB-2 may worsen hepatitis C. Patients with hepatitis B are not excluded if on Lamivudine, which is used to prevent reactivation/worsening of hepatitis B with chemotherapy and other immunosuppressive treatments. Patients that are pregnant or breast-feeding will be excluded from this trial because the effect of LMB-2 on the developing fetus or the nursing infant is unknown and potentially harmful.

5.2 PARTICIPATION OF CHILDREN

Only patients 18 years of age or older will be enrolled on this study, since the safety of this agent has not been previously defined in a pediatric population.

5.3 PARTICIPATION OF SUBJECTS UNABLE TO CONSENT

Adults unable to give consent are excluded from enrolling in the protocol. However, re-consent may be necessary and there is a possibility, though unlikely, that subjects could become

decisionally impaired. For this reason and because there is a prospect of direct benefit from research participation (section **5.5**), all subjects will be offered the opportunity to fill in their wishes for research and care, and assign a substitute decision maker on the “NIH Advance Directive for Health Care and Medical Research Participation” form so that another person can make decisions about their medical care in the event that they become incapacitated or cognitively impaired during the course of the study. Note: The PI or AI will contact the NIH Ability to Consent Assessment Team(ACAT) for evaluation to assess ongoing capacity of the subjects and to identify an LAR, as needed.

Please see Section **5.6.1** for consent procedure.

5.4 EVALUATION OF BENEFITS AND RISKS/DISCOMFORTS

5.4.1 Potential benefits to subjects expected from the trial

Patients will receive evaluation and treatment of their tumor at the National Cancer Institute’s Clinical Center. This protocol may or may not benefit an individual, but the results may help the investigators learn more about the disease and develop new treatments for patients with this disease. Benefit cannot be promised nor can the chance of benefit be accurately predicted. This research treatment is unlikely to be curative but may offer temporary control of the disease.

5.4.2 Alternative approaches or treatments

Patients will be consented verbally and in writing regarding the risks and benefits of this trial, the treatment requirements, and alternative approaches to entering on this trial.

5.4.3 Procedures for protecting against or minimizing any potential risks

All care will be taken to minimize side effects, but they can be unpredictable in nature and severity. This study may involve risks to patients which are currently unforeseeable. Patients will be examined and evaluated prior to enrollment and prior to each cycle. The Clinical Center staff will observe all patients during the drug administration. All evaluations to monitor the treatment of patients will be recorded in the patient chart. Patients are required to have a local physician to improve long-term care and to monitor for complications. They will have blood draws at home to monitor side effects. If patients suffer any physical injury as a result of the participation in this study, immediate medical treatment is available at the Clinical Center, National Cancer Institute, Bethesda, Maryland. Although no compensation is available, any injury will be evaluated and treated in keeping with the benefits or care to which patients are entitled under applicable regulations.

5.4.4 Identified Risks to Study Procedures

5.4.4.1 Blood Sampling

Side effects of blood draws include pain and bruising, lightheadedness, and rarely, fainting.

5.4.4.2 Imaging

In addition to the radiation risks discussed below, CT scans may include the risks of an allergic reaction to the contrast. Participants might experience hives, itching, headache, difficulty breathing, increased heartrate and swelling.

5.4.4.3 MR Imaging

The risks of MR imaging are relatively small.

The US Food and Drug Administration has issued warnings that administration of gadolinium (updated September 9, 2010), the MRI contrast imaging agent used in this protocol, has been associated with development of a disease called **nephrogenic systemic fibrosis (NSF)**. The syndrome is rare (approximately 600 cases reported worldwide as of September 2010, out of several million administrations of gadolinium), but disabling and in some cases, fatal. All cases to date have occurred in patients with severe renal disease, including patients on dialysis. NSF has been nearly eradicated secondary to careful screening of renal function and avoiding use of gadolinium in patients with eGFR <30 ml/min/1.73 BSA. Even in patients with end stage renal disease, there have been only rare occurrences of NSF because of precautions taken to use more stable contrast agents at lower doses. This protocol excludes patients with severe renal insufficiency (eGFR <30 ml/min/1.73 BSA). The FDA has issued warnings in 2017 and 2018 that some gadolinium may be retained in the brain, bone and skin although health risks of accumulation have not been reported to date. In accordance with the FDA Drug Safety Communication of 05/16/2018, the Medication Guide for gadobutrol (or other macrocyclic gadolinium contrast agent if applicable) will be made available to all subjects with scans that will involve gadolinium-based contrast agent administration.

5.4.5 Risks from Radiation Exposure

On this study, participants will receive up to 4 CT scans/year. The total radiation dose for research purposes will be approximately 5.2 rem. The risk of getting cancer from the radiation exposure in this study is 0.5% and of getting a fatal cancer is 0.3%.

5.4.6 Provisions for monitoring data collection to ensure safety of subjects

As information is gathered from this trial, clinical results will be shared with patients while maintaining patient confidentiality. Laboratory and clinical data will be frequently gathered and any new significant findings found during the course of the research, which may affect a patient's willingness to participate further, will be explained. Moreover, in all publications and presentations resulting from this trial, patients' anonymity will be protected to the maximum extent possible. Authorized personnel from the National Cancer Institute (NCI) and Food and Drug Administration (FDA) may have access to research files in order to verify that patients' rights have been safeguarded. In addition, patient names will be given to the Central Registration to register and verify patients' eligibility.

Primary and final analyzed data will have identifiers so that research data can be attributed to an individual human subject participant.

End of study procedures: Data will be stored according to HHS, FDA regulations and NIH Intramural Records Retention Schedule as applicable.

5.5 RISKS/BENEFITS ANALYSIS

Patients enrolled on this study will be those with a disease that is considered incurable. They will generally have a poor prognosis and have no standard treatment options known to significantly improve survival. Thus, patients may experience significant treatment related morbidity, and/or have progressive complications of their disease. Although LMB-2 is an experimental new immunotoxin, another drug with a similar mechanism of action and similar toxicities was recently approved for CTCL. In addition, we have seen responses to LMB-2 in patients with CLL and HCL with acceptable toxicities. Consequently, we believe that patients participating in this trial will have an acceptable benefit/risk ratio.

5.6 CONSENT PROCESS AND DOCUMENTATION

The informed consent document will be provided as a physical or electronic document to the participant or consent designee(s) as applicable for review prior to consenting. A designated study investigator will carefully explain the procedures and tests involved in this study, and the associated risks, discomforts and benefits. In order to minimize potential coercion, as much time as is needed to review the document will be given, including an opportunity to discuss it with friends, family members and/or other advisors, and to ask questions of any designated study investigator. A signed informed consent document will be obtained prior to entry onto the study.

The initial consent process as well as re-consent, when required, may take place in person or remotely (e.g., via telephone or other NIH approved remote platforms used in compliance with policy, including HRPP Policy 303) per discretion of the designated study investigator and with the agreement of the participant/consent designee(s). Whether in person or remote, the privacy of the subject will be maintained. Consenting investigators (and participant/consent designee, when in person) will be located in a private area (e.g., clinic consult room). When consent is conducted remotely, the participant/consent designee will be informed of the private nature of the discussion and will be encouraged to relocate to a more private setting if needed.

Consent will be documented with required signatures on the physical document (which includes the printout of an electronic document sent to participant) or as described below, with a manual (non-electronic) signature on the electronic document. When required, witness signature will be obtained similarly as described for the investigator and participant.

Manual (non-electronic) signature on electronic document:

When a manual signature on an electronic document is used for the documentation of consent at the NIH Clinical Center, this study will use the following to obtain the required signatures:

- Adobe platform (which is not 21 CFR Part 11 compliant); or,
- iMedConsent platform (which is 21 CFR Part 11 compliant)

During the consent process, participants and investigators will view individual copies of the approved consent document on screens at their respective locations (if remote consent); the same screen may be used when in the same location but is not required.

Both the investigator and the participant will sign the document using a finger, stylus or mouse.

Note: Refer to the CCR SOP PM-2, Obtaining and Documenting the Informed Consent Process for additional information (e.g., verification of participant identity when obtaining consent remotely) found at:

<https://ccrod.cancer.gov/confluence/pages/viewpage.action?pageId=73203825>.

5.6.1 Consent Process for Adults Who Lack Capacity to Consent to Research Participation

For participants addressed in Section **5.3**, an LAR will be identified consistent with Policy 403 and informed consent obtained from the LAR, as described in Section **5.6**.

5.6.2 Consent to obtain samples for eligibility

The patient must give informed consent even before protocol enrollment, at the time that samples are taken to test eligibility. A separate informed consent is given to the patient clarifying what tests will be done and stating that no germline testing is to be done. This eligibility informed consent also states that the patient may eventually not be considered a candidate for the study. The eligibility consent may be signed by the patient prior to arrival at NIH, but the actual treatment (standard) consent must be signed in person prior to protocol enrollment.

5.7 SAMPLE STORAGE, TRACKING AND DISPOSITION

5.7.1.1 Description of data/specimens: Blood, bone marrow, lymph node, skin, and other tumor samples.

5.7.1.2 Research being conducted: Samples to be saved for additional tests:

- Neutralizing antibodies: Antibodies a patient might make which block the effect of certain recombinant immunotoxins like LMB-2. Requires about 6 ml of blood.
- Flow cytometry assays to quantify tumor markers on the malignant cells. Requires about 3 ml of blood.
- Bone marrow biopsy samples, whether they obtained at NIH or elsewhere, and whether the bone marrow test has already been done or not yet done.
- Cytotoxicity assays. Leukemia cells from the blood, bone marrow, or other tissues may be tested with LMB-2 and related drugs to determine if the malignant cells can be killed outside the body. Requires 15-45 ml of blood.
- Soluble CD25, CD22, and other tumor markers: To estimate the amount of cancer cells in the body by measuring proteins which fall off cancer cells and go into the blood. Requires about 6 ml of blood.
- HLA typing to better understand the immune system in patients with hairy cell leukemia. Requires about 6 ml of blood.
- PAX-gene tube: To obtain RNA or DNA to study the mechanism of how leukemia cells form, and to detect very low levels of leukemia cells in patients. Requires about 3 ml of blood.
- RNA samples can also be used, in an assay called micro-arrays, to study why some patients may not respond as well as others to recombinant immunotoxins like LMB-2. Taken with PaxGene tube.

- Samples of blood to study how hemolytic uremic syndrome (HUS), a major toxicity of a recombinant immunotoxin called BL22, which is similar to LMB-2, occurs and might be prevented. Requires about 3 ml of blood.
- DNA samples to look for abnormalities which might make a patient more susceptible to HUS. Requires about 3 ml of blood.
- Assays which could have an impact on both patients and their children, including studies of genetic cancer risk, will not be done.
- Samples to determine levels of immunotoxin in blood, urine, and other tissues.

5.7.1.3 Timeframe and location of storage: Samples will be stored and cataloged longer than a year, in alarmed freezers at our Leidos Biomedical Research, Inc. contract lab in Frederick, MD, where neutralizing antibodies and PK samples are tested. Portions of samples which are stored at Leidos Biomedical Research, Inc. in Frederick may also be stored and tested in the LMB lab (Building 37) for longer than a year providing there is sample remaining after studies are done. All samples will be stored with unique patient numbers and without personal identifiers. After closure of the protocol, the samples will either be destroyed or their storage and use will be governed by a subsequent protocol. Samples at Leidos Biomedical Research, Inc. in Frederick will be tracked in a secure electronic database and the PI will report lost or destroyed samples per the requirements of Section [8.2](#).

6 DOSING DELAYS/DOSE MODIFICATION

6.1 NO DLT

Continue treatment or retreatment at same dosage.

6.2 DLT

This also applies to patients undergoing retreatment cycles.

6.2.1 Off Treatment for DLT from:

- Grade III Allergic Reaction and grade II urticaria despite premedication.
- Grade IV toxicity other than hematologic and CPK.
- Grade IV hematologic toxicity lasting > 5 days.
- Grade IV CPK associated with any other DLT or not resolving to < grade II within 2 weeks.

6.2.2 Requiring dose reduction if retreating after DLT from:

- Grade III toxicities except for AST, ALT, GGT, and hematologic.
- Grade IV CPK not associated with any other DLT and resolving to < grade II within 2 weeks.

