3.2 RESEARCH ELIGIBILITY EVALUATION

- A blood sample will be submitted to the NIH pathology department for analysis of CD25 expression (an eligibility criterion) by FACS analysis. This analysis will be done in the Laboratory of Pathology, NIH (Anatomic Pathology Dept., CC), a College of American Pathologists (CAP) and CLIA-approved laboratory, by standardized diagnostic techniques.
- Complete history and physical examination with documentation of measurable disease (lymph nodes, spleen, liver), stage, and performance status within 2 weeks before starting LMB-2. Physical examination should record the diameter, in two planes, of the largest palpable nodes in each of the following sites: cervical, axillary, supraclavicular, inguinal, and femoral. Physical examination should record liver and spleen size as determined by measurement below the respective costal margin.

- ECG and CXR within 3 days before starting LMB-2.
- CT scan of the chest, abdomen, and pelvis, or abdominal MRI, within 4 weeks before starting LMB-2.
- Serum anti-LMB-2 antibody assay, HIV, Hepatitis B surface antigen, and hepatitis C screen within 2 months before starting LMB-2.
- Laboratory evaluation within 2 weeks before starting LMB-2 will include CBC/differential, acute care panel (electrolytes, glucose, BUN, creatinine), hepatic panel (AST, ALT, Alkaline phosphatase, total and direct bilirubin), albumin, LDH, PT, Beta 2 microglobulin (B2M), serum protein electrophoresis (SPEP), urinalysis, and a 24 urine creatinine clearance and total protein. A CBC/differential, acute care panel, hepatic panel, and albumin must be done within 3 days of starting cycle 1.
- Urine or serum pregnancy test within 72 hours before starting LMB-2 in women with childbearing potential.
- Bone marrow biopsies and echocardiogram with left ventricular ejection fraction calculation, and stress test, will be done on all patients within 2 months before starting LMB-2.

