4.2.3 Treatment Modifications for Toxicities on Current Cycle

Treatment should not be given on Day 3 or 5 until the laboratory values are reviewed for creatinine, AST, ALT, and GGT to determine if treatment modifications are necessary.

Grades I and II Allergic Reaction/hypersensitivity (including drug fever):

- Drug fever only: give acetaminophen every 4-6 hours until resolved (see section 4.8).
- Rash (under Allergic reaction in CTC 3.0 to be utilized until December 31, 2010 and under Skin and Subcutaneous Tissue Disorder in CTCAE 4.0 to be utilized after January 1, 2011): follow guidelines in section 4.8 and hold treatment (up to 3 days) until symptoms resolve.

Grade II Creatinine: Drug will be held (up to 3 days) until Creatinine is \leq Grade I.

Grade III Allergic Reaction or Grade II Allergic Reaction with asymptomatic bronchospasm or urticaria: Stop treatment. Off treatment (DLT).

Other grade III toxicities except for AST, ALT, GGT, and hematologic: Stop treatment. Cycle ends (DLT).

Grade IV toxicities except for grade 4 hematologic toxicity lasting \leq 5 days: Stop treatment. Off treatment (DLT).

Grade IV hematologic toxicity lasting $>$ 5 days except for alopecia: Off treatment (DTL).

Grade IV CPK associated with any other DLT or not resolving to $<$ grade II within 2 weeks: Off treatment (DLT).

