4.4.2 Routine Tests done during Each Cycle

4.4.2.1 Days 3, 5

CBC/diff, acute care panel, hepatic panel, mineral panel, LDH, urinalysis, uric acid, CK.

4.4.2.2 Weeks 2 and 3

The following labs will be drawn once during weeks 2 and 3: CBC/diff, acute care panel, hepatic panel, and albumin.

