4.7 RETREATMENT

Patients without evidence of progression and without sufficient neutralizing antibodies will be eligible to receive retreatment cycles of LMB-2 at the same dose with at least 25 days between cycles. Patients will be tested for neutralizing antibodies prior to each cycle. Treatment may not continue for beyond two cycles for a complete response (CR), beyond four cycles for CR with minimal residual disease (MRD), or beyond six cycles for a partial response (PR) or stable disease (SD) without prior FDA approval.

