4.9.1 Criteria for removal from protocol therapy

- Progression of disease during active treatment on study protocol.
- Grade III Allergic Reaction and grade II urticaria despite premedication.
- More than 2 dose reductions are required.
- Patient non-compliance or voluntary withdrawal.
- Patient's serum neutralizes $> 75\%$ of the activity of 1 $\mu\text{g}/\text{mL}$ of LMB-2.
- Grade IV toxicity other than hematologic and CPK.
- Grade IV hematologic toxicity lasting > 5 days.
- Grade IV CPK associated with any other DLT or not resolving to $<$ grade II within 2 weeks.

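### No CK is scheduled between the day 5 draw and the next pre-cycle visit, so a CPK rise after the third dose can go unmeasured before same-dose retreatment

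*Combined protocol and SAP*

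**What the plan says.** **Schedule.** Section 4.4.1 puts CK among the pre-cycle labs, taken on day 1 or up to 3 days before it. Section 4.4.2.1 lists for days 3 and 5: "CBC/diff, acute care panel, hepatic panel, mineral panel, LDH, urinalysis, uric acid, CK". For the following two weeks, 4.4.2.2 says: "The following labs will be drawn once during weeks 2 and 3: CBC/diff, acute care panel, hepatic panel, and albumin". Section 3.2 gives the panel contents as "acute care panel (electrolytes, glucose, BUN, creatinine), hepatic panel (AST, ALT, Alkaline phosphatase, total and direct bilirubin", so neither panel contains CK. The CK row of the Study Calendar (Section 12) agrees: pre-cycle, day 3 and day 5 only.

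**Dosing.** LMB-2 is given on days 1, 3 and 5. Section 4.2.3 withholds the day 3 and day 5 doses until creatinine and liver enzymes have been reviewed, so that day's labs precede the dose.

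**Rules for CPK.** Sections 4.9.1 and 6.2.1, and a dedicated line in 4.2.3, take a patient off treatment if grade IV CPK accompanies another DLT or has not fallen below grade II within 2 weeks. Section 6.2.2 requires dose reduction instead for "Grade IV CPK not associated with any other DLT and resolving to < grade II within 2 weeks". It also requires reduction for grade III toxicities other than AST, ALT, GGT and hematologic, which includes grade III CPK. With no DLT, 6.1 says "Continue treatment or retreatment at same dosage", and 4.7 allows "retreatment cycles of LMB-2 at the same dose with at least 25 days between cycles".

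**General grade IV line.** Section 4.2.3 takes patients off treatment for "Grade IV toxicities except for grade 4 hematologic toxicity lasting" 5 days or less. The matching line in 4.9.1, repeated in 6.2.1, reads "Grade IV toxicity other than hematologic and CPK".

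**The concern.** The dose rules act on CPK grade and on how quickly CPK resolves, but the schedule stops measuring CK before the last dose of the cycle has been given. Two things follow.

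First, a rise caused by dose 3 that has settled by the next pre-cycle visit leaves no record. The patient counts as having no DLT and is retreated at the same dose, where 6.2.2 would have required a reduction (from 40 to 30 µg/Kg at the first step, 4.2.5).

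Second, when a grade IV value is seen on day 5, the choice between removal (6.2.1) and reduction (6.2.2) depends on whether it resolves within 2 weeks, and no scheduled test falls in that period.

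The protocol treats CPK as worth acting on. One grade IV elevation, in a CTCL patient, led that trial to lower its dose to 30 µg/Kg (2.5), and 10.1.2.2 lists CK elevation among the grade III-IV toxicities seen. At stake are patient safety and consistent dosing. The response-rate analysis is not affected.

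**Working it through.** The plan gives no figure to reproduce here. The check is a day count.

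**Inputs.** CK on days 3 and 5 (4.4.2.1). Pre-cycle CK 0 to 3 days before the next day 1 (4.4.1). Cycle interval 28 days, minimum 25 (4.1), or at least 25 days between cycles (4.7). CPK window 14 days (4.2.3, 4.9.1, 6.2).

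**Step 1: next scheduled CK after day 5.** The minimum interval can be read in more than one way, so each reading is shown. The CK falls from (next day 1 − 3) to next day 1. The gap is that day minus 5.

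| Reading of the interval | Next day 1 | Pre-cycle CK | Days since day 5 |
|---|---|---|---|
| 25 days, counted inclusively | 25 | 22-25 | 17-20 |
| 25 days, day 1 to day 1 | 26 | 23-26 | 18-21 |
| Nominal 28 days | 29 | 26-29 | 21-24 |
| 25 days after the day 5 dose | 30 | 27-30 | 22-25 |

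The shortest gap is 22 − 5 = 17 days. There is no upper limit, because 25 days is a minimum and 6.3 permits delays.

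**Step 2: the 2-week window.**
- Grade IV first seen on day 5: the window closes on day 5 + 14 = 19. No scheduled CK lies inside it. The next comes at least 22 − 19 = 3 days after it closes, or 7-10 days after on the 28-day cycle (26 − 19 to 29 − 19).
- Grade IV first seen on day 3: the window closes on day 3 + 14 = 17. The day 5 CK lies inside it, 2 days after the first value. After that, nothing is scheduled until day 22 at the earliest.

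**Step 3: effect of adding CK to the week 2 and week 3 draws.** Take week 2 as days 8-14 and week 3 as days 15-21, with one draw in each week as the calendar shows.
- The first CK after dose 3 moves to 8 − 5 = 3 up to 14 − 5 = 9 days after day 5, instead of at least 17.
- The week 2 draw always lies inside the 2-week window, but it may come too early to show resolution.
- The week 3 draw lies inside the window on days 15-17 for a day 3 onset (3 of 7 possible days) and on days 15-19 for a day 5 onset (5 of 7).

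The routine draws therefore cover most of the unmonitored interval but cannot guarantee a test near the end of the window. That needs a repeat triggered by the event.

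**The case against.** **A known grade IV value would not be ignored.** A rule that asks whether CPK resolved within 2 weeks implies a repeat test, and a clinician would probably order one. Other provisions point the same way:
- 4.2.4 requires recovery to grade I or less before retreatment, the same threshold as below grade II, so a known unresolved CPK cannot be re-dosed.
- No grade 4 event is expected (7.4.1.1), so a grade IV CPK needs expedited reporting (7.3.2).
- The team discusses each participant at least weekly (8.4), adverse events carry a resolution date (7.4), and patients off treatment for toxicity are followed until it resolves (4.10).

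This stands, and it reduces the 2-week problem to choosing between removal and reduction without a required, dated test. It does not help with a rise that nobody measured.

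**No evidence shows that late rises occur.** The documents give no timing for CPK elevations. Four of 5 CLL patients tolerated 40 µg/Kg without DLT, and the protocol regards HCL as closer to CLL (2.5). Creatinine is drawn in weeks 2 and 3, so a renal effect could be noticed, and grade II creatinine itself forces a reduction (4.2.4). This also stands, and it keeps the priority modest.

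**Stronger readings that the documents do not support.**
- A reader might infer that the next CK always comes too late for the 2-week rule. For a day 3 onset the day 5 CK is inside the window, so this holds only for tests after day 5.
- A reader might take the absence of a CPK row in Table 2 as none of 12 patients and derive a limit on the rate. The available text of the table is broken and the pages before it are missing, so no rate can be taken from it. It would in any case not describe rises that were never measured.
- A reader might conclude that 4.2.3 removes every patient with grade IV CPK. Its general line, read literally, does. However, its own CPK line and the explicit exemptions in 4.9.1 and 6.2.1 largely settle the intent, so only a wording repair is needed.

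**Conclusion.** The point holds in this form: the interval after the third dose has no scheduled CK for at least 17 days, and for 21-24 days on the nominal cycle. A patient followed exactly to plan can therefore have a transient grade III-IV CPK rise, go unrecorded, and be retreated at the same dose although 6.2.2 calls for a reduction. The 2-week rule also lacks a scheduled test for a day 5 onset, and has only the day 5 test for a day 3 onset. That part matters less, because a known value would in practice be repeated.

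This rests on two assumptions: that the day 5 CK is taken with the labs reviewed before that day's dose, and that no unscheduled CK is ordered. If the day 5 sample were instead taken later the same day, it would still be too early to follow the effect of dose 3. The schedule gap is certain. The frequency of late rises, and hence the amount of harm avoided, is unknown. This is a cheap safety improvement of modest priority.

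**What to change.** 1. Add CK to the existing week 2 and week 3 draws, in 4.4.2.2 and in the Study Calendar.
2. In 6.2, require a repeat CK by 14 days after onset of any grade IV CPK, and use it to choose between 6.2.1 and 6.2.2.
3. As a tidy-up in the same amendment, exempt CPK from the general grade IV off-treatment line in 4.2.3, to match 4.9.1 and 6.2.1.

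**Cost.** Two extra assays per cycle on blood already being drawn: 2 × 6 = 12 per patient over six cycles, or 2 × 10 = 20 if four consolidation cycles follow. For 25 evaluable patients that is 25 × 12 = 300 to 25 × 20 = 500 assays before any retreatment after relapse, plus an occasional triggered test and a short amendment. The downside is that more CPK events will be found, with more doses held or reduced. A rise that comes and goes between two weekly draws could still be missed.
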